10.5.2 Efficacy Analysis

10.5.2.1 Primary Endpoint

To evaluate the efficacy of TS-121 compared to placebo on MDD symptoms in MDD patients, Mixed Model Repeated Measures analysis (MMRM)/non-parametric methods will be used to compare the difference between the three treatment groups on the primary endpoint (change in MADRS score) depending on the distribution of the data. On the primary endpoint (change in MADRS score), as assessed at Week 6, a statistically significant GROUP*TIME interaction effect, with greater reductions in MADRS scores in the TS-121 groups, will be interpreted as indicating efficacy (GROUP: Placebo, TS-121 10 mg and TS-121 50 mg, TIME: Week 2, Week 4 and Week 6).

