# Statistical Analysis Plan

Taisho Pharmaceutical R&D Inc.  
Protocol TS121-US201

Statistical Analysis Plan (SAP)

Final 2.0  
18 Dec 2018  
CONFIDENTIAL

In case an unscheduled clinical laboratory assessment was performed within the visit window for a missing assessment then the unscheduled assessment will be included in the visit summary. In these cases the unscheduled assessment closest to the scheduled time will be used.

Missing data are assumed to be missing at random (MAR).

The primary endpoint for efficacy is Week 6/EOT. Efficacy assessments are not planned to be collected at early termination. The primary analysis will include all available efficacy assessments of the Intent to Treat Population. The primary analysis will use MMRM, in which patients with no post baseline assessment are dropped from the model. A sensitivity analysis will assess the Week 6/EOT of each efficacy endpoint (MADRS total score, CGI, HAM-A total score and SDQ total score) based on a multiple imputation method using all patients with a baseline score, including patients with no post baseline assessment.

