# Statistical Analysis Plan

Taisho Pharmaceutical R&D Inc.  
Protocol TS121-US201

Statistical Analysis Plan (SAP)

Final 2.0  
18 Dec 2018  
CONFIDENTIAL

Treatment group mean (+/- SE) MADRS total score and total score change from baseline will be plotted versus treatment [Figure 14.2.2.1 and Figure 14.2.2.2].

To evaluate the efficacy of TS-121 compared to placebo on MDD symptoms as measured by the MADRS scale, Mixed Model Repeated Measures analysis (MMRM)/non-parametric methods will be used to compare the difference between the three treatment groups on the primary endpoint (change from baseline in MADRS score) depending on the distribution of the data. The baseline MADRS total score will be included as a covariate. Comparisons of TS-121 10 mg versus placebo and TS-121 50 mg versus placebo will be evaluated at each timepoint.

The following is example SAS programming code that will be used to fit the MMRM model and evaluate treatment mean differences:

```
Proc Mixed Method = REML;  
    Class GROUP Subject_ID VISIT;  
    Model Change = Baseline GROUP VISIT GROUP*VISIT  
        / solution ddfm=kenwardroger;  
    repeated VISIT / sub=Subject_ID type= UN;  
    lsmeans GROUP*VISIT / pdiff alpha=0.05 cl;  
    ods output lsmeans=lsm covparms=cp tests3=t3 diffs=diffs;  
  
run; quit;
```

In case the repeated measures model with unstructured covariance matrix (type = UN) fails to converge then the compound symmetry model (type = CS) will be used.

Least squares treatment group mean differences with 95% confidence intervals will be reported for TS-121 10 mg versus placebo and for TS-121 50 mg versus placebo evaluated at Visits 4, 5, 6/EOT and 7. The primary endpoints for analysis are treatment mean differences at Week 6/EOT [Table 14.2.2.3]. Statistical significance of Type 3 tests and model variance terms will be reported separately [Table 14.2.2.4].

The primary analysis will assess treatment mean differences at Week 6/EOT. An assessment of time on treatment will be performed as an analysis of covariance on the latest assessment of the primary endpoint, change in MADRS score. The model will include all patients in the specified population and may include patients with the baseline assessment and no post-baseline efficacy data. In this model, where TIME will be included as a continuous predictor in this model, a

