## Table 2 Tables to be Included in Section 14 of the Clinical Study Report

*Note: Top line tables are indicated \**

---

SECTION 14.1:	Demographic Data
*Table 14.1.1.1	Patient Disposition by Treatment Group and Overall (All Randomized Patients)
Table 14.1.1.2	Patient Disposition by Treatment Group and Overall (Safety Analysis Population)
Table 14.1.1.3	Patient Disposition Through End of Placebo Lead-in (All Consented Patients)
Table 14.1.2.1	Demographics and Baseline Characteristics including Screening Height, Weight and Body Mass Index (Safety Analysis Population)
*Table 14.1.2.2	Hamilton Depression Scale HAM-D Total Score at Screening and Baseline (Safety Analysis Population)
*Table 14.1.3	Baseline Major Depressive Disorder Characteristics (Safety Analysis Population)
Table 14.1.4	Medical History and Psychiatric History (Safety Analysis Population)
Table 14.1.5	Concomitant Medications (Safety Analysis Population)
SECTION 14.2:	Treatment Compliance, PK, Efficacy and PD Data
Table 14.2.1	Treatment Dose Compliance (Safety Analysis Population)
*Table 14.2.2.1	Montgomery-Asberg Depression Rating Scale (MADRS) Total Score Observed and Change from Baseline by Treatment and Visit (Intent to Treat Population)
Table 14.2.2.2	Montgomery-Asberg Depression Rating Scale (MADRS) Item Response Frequency by Treatment and Visit (Intent to Treat Population)
*Table 14.2.2.3	Analysis of Montgomery-Asberg Depression Rating Scale (MADRS) Total Score Change from Baseline Least Squares Treatment Mean Differences by Visit (Intent to Treat Population)
Table 14.2.2.3.1	Multiple Imputation Method for Missing Visits Analysis of Montgomery-Asberg Depression Rating Scale (MADRS) Total Score Change from Baseline Least Squares Treatment Mean Differences by Visit (Intent to Treat Population)
*Table 14.2.2.4	Analysis of Montgomery-Asberg Depression Rating Scale (MADRS) Total Score Change from Baseline Model Summary (Intent to Treat Population)
Table 14.2.2.4.1	Multiple Imputation Method for Missing Visits Analysis of Montgomery-Asberg Depression Rating Scale (MADRS) Total Score Change from Baseline Model Summary (Intent to Treat Population)
*Table 14.2.2.5	Analysis of Montgomery-Asberg Depression Rating Scale (MADRS) Total Score Change from Baseline at Week 6/EOT (Intent to Treat Population)
Table 14.2.2.6	Montgomery-Asberg Depression Rating Scale (MADRS) Responders Comparison of TS-121 Treatment versus Placebo at Week 6/EOT (Intent to Treat Population)

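### The SAP's only MADRS MMRM includes the off-treatment Visit 7, so its top-line Type 3 tests are not the Weeks 2, 4 and 6 tests that the protocol describes (low severity)

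*SAP*

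**What the plan says.** Protocol 10.5.2.1 lists the levels of the time factor as "TIME: Week 2, Week 4 and Week 6". Its decision sentence is that "a statistically significant GROUP*TIME interaction effect, with greater reductions in MADRS scores in the TS-121 groups, will be interpreted as indicating efficacy". The SAP repeats the same three levels in its section on the amended plan, as an Amendment 4 change that affects data presentation.

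SAP 6.3.13.1 gives one repeated-measures model, "Model Change = Baseline GROUP VISIT GROUP*VISIT", and takes its differences from "lsmeans GROUP*VISIT / pdiff alpha=0.05 cl". It reports them for "TS-121 10 mg versus placebo and for TS-121 50 mg versus placebo evaluated at Visits 4, 5, 6/EOT and 7". It names the Week 6/EOT differences as primary and adds that "Statistical significance of Type 3 tests and model variance terms will be reported separately", in Table 14.2.2.4. SAP Table 2 marks that table as top-line.

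Visit 7 is off treatment. Protocol 8.4 ends the treatment period at Visit 6, the protocol synopsis places Visit 7 about two weeks later, and SAP 6.3.1 classes anything after Week 6/EOT as follow-up. SAP 6.3.4 states "Efficacy assessments are not planned to be collected at early termination", and the schedule shows no efficacy scale in the early-termination columns. Visit 7 scores will therefore come mainly from patients who completed treatment.

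**The concern.** The protocol's interaction asks whether the groups separate over three visits on randomized drug. The SAP output closest to it, the MMRM Type 3 GROUP*VISIT test, asks whether they differ over four visits, one of them off drug. A reader who takes the protocol's rule to Table 14.2.2.4 would be reading a different hypothesis. Loss of effect after stopping could produce a significant interaction even if the on-drug difference was constant. The Type 3 GROUP test would also be diluted by a visit at which nobody takes the drug. The same model form serves CGI-S, HAM-A and SDQ (SAP 6.3.13.2) and is rerun after multiple imputation (SAP 6.3.13.3), so the mismatch carries over to those results.

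**Working it through.** **No plan figure to reproduce.** Protocol 10.1 and SAP section 5 say that the sample size does not rest on a power calculation. Neither document gives an effect size or SD.

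**1. Does Visit 7 enter the model?** The SAP code is an example and shows no data filter, so this is an inference. It is a firm one. An lsmeans difference at Visit 7 needs Visit 7 rows in the model, SAP 6.3.4 admits all available efficacy assessments, and the imputation step carries FOLLOW before the same MMRM is rerun.

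**2. Structure (no assumptions about the data).** With 3 groups and V visits:
- GROUP*VISIT numerator df = (3 − 1)(V − 1). This is 4 for V = 3 and 6 for V = 4.
- The Type 3 GROUP test weights each visit 1/V. With V = 4, one quarter of the weight is off drug. A benefit d at all three on-drug visits and e at Visit 7 enters as (3d + e)/4 instead of d.

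**3. Illustration.** All inputs are assumed except three from the documents: 60 per arm as the upper sample size (protocol synopsis), 1:1:1 allocation and the two-sided 5% level (SAP 6.3.2). SDs are 7.5, 8.5, 9 and 9 at Visits 4 to 7. Correlation is AR 0.7, AR 0.8 or CS 0.6. There are 51 or 60 per arm, the data are complete, the covariance is known, and both active arms have the same effect. Power comes from a noncentral F with 3n − 4 denominator df and:
- GROUP: λ = (2n/3)(mean difference ÷ SD of the visit mean)².
- GROUP*VISIT: λ = (2n/3) δ′(CΣC′)⁻¹δ, where δ holds the differences between visits in the treatment effect.

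Case: 3 points at Weeks 2, 4 and 6, and 0 at Visit 7. Take AR 0.7 and 51 per arm:
- GROUP, three visits: λ = 34 × (3 ÷ 7.24)² = 5.8, power 56%.
- GROUP, four visits: the mean effect is (3 × 3 + 0)/4 = 2.25, so λ = 34 × (2.25 ÷ 7.02)² = 3.5, power 36%.
- GROUP*VISIT, three visits: δ = 0, so rejection is 5%.
- GROUP*VISIT, four visits: λ = 6.7, rejection 43%.

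| Test (range over all six settings) | Visits 4-6 | Visits 4-7 |
|---|---|---|
| GROUP | 52%-65% | 32%-42% |
| GROUP*VISIT | 5% | 43%-70% |

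**4. Less extreme off-drug patterns.**
- Half the effect lost (1.5 points at Visit 7): δ halves, so the GROUP*VISIT λ falls to a quarter (6.7 to 1.7 in the worked setting). Rejection over the six settings is 0.125 to 0.192.
- Effect fully persists: δ = 0, so GROUP*VISIT stays at 5%. GROUP λ in the worked setting rises from 5.8 to 34 × (3 ÷ 7.02)² = 6.2, and power goes from 56% to 59%.
- Effect of 1, 2 and 3 points on drug, then 3 at Visit 7, same setting: GROUP power goes from 0.28 to 0.36.

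**5. The Week 6 contrast.** This was simulated in 400 trials: 60 per arm, SD 9, AR 0.75, about 6% dropout per visit, 3% missing Visit 6 only, effects of 1, 2, 3 and then 0 points, fixed working covariance. The mean difference was −2.90 with or without Visit 7, and the empirical SE was 1.79 both ways. The SD of the within-trial shift was about 0.13 point (working covariance equal to the simulated one) and 0.08 (compound symmetry).

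**The case against.** The strongest reply is that nothing decisive depends on these tests, and most of it stands.

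- The SAP's primary result is the Week 6/EOT difference, which Visit 7 barely moves. A reader might infer that the primary estimate is compromised. It is not.
- The SAP attaches its own GROUP*TIME efficacy statement to a separate ANCOVA with continuous TIME (Table 14.2.2.5). The MMRM Type 3 tests are only reported.
- Neither document gives the GROUP main effect a decision role, so its loss of power changes no stated conclusion.
- A reader might infer a risk of falsely claiming efficacy. With no on-drug effect and a 3-point worsening after stopping, δ has the same size as in step 3, so GROUP*VISIT again rejects in 43% to 70%. But the protocol also requires greater MADRS reductions on TS-121, which that pattern does not show, so its rule largely excludes the claim. In the constant-benefit case the drug does work, so a significant interaction is not a false claim of efficacy, although it arises only from loss of effect off drug.
- The large figures assume complete loss of effect in both dose arms by Visit 7, and the documents give no rate of offset.
- Visit 7 efficacy is a planned assessment and the study is a pilot, so a modelled Visit 7 estimate has some use.

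The mismatch itself remains. The protocol names three time levels, the SAP quotes them and then fits four, and it sends the resulting tests to a top-line table without saying how to read them.

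**Conclusion.** The point holds as a low-severity inconsistency between protocol and SAP. The change in degrees of freedom and the one-quarter off-drug weight follow from the specification once Visit 7 rows are in the model. The rejection rates are illustrations. They rest on assumed SDs, correlations and effects, and they shrink quickly if the effect fades only partly. If it persists, GROUP power is unchanged or slightly higher.

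A reader might also infer that the larger unstructured matrix (10 covariance parameters instead of 6) makes the fallback to compound symmetry more likely. That has not been shown: no convergence failure was simulated, and 10 parameters is modest for about 180 patients.

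**What to change.** In SAP 6.3.13.1, state that the MADRS MMRM supplying the Type 3 tests uses Visits 4, 5 and 6 only, to match the protocol's time factor. Apply the same restriction to the CGI-S, HAM-A and SDQ models and to the MMRM refitted after multiple imputation. Report Visit 7 in the descriptive tables or in a separate supportive model. FOLLOW can stay in the imputation step as an auxiliary variable if wanted.

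The cost is a sentence of SAP text and a visit filter in the program. The downside is one extra model run per scale if a modelled Visit 7 difference is wanted. If the four-visit model is kept, the minimum is a statement that no efficacy inference is drawn from its Type 3 tests.

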# Statistical Analysis Plan

Taisho Pharmaceutical R&D Inc.  
Protocol TS121-US201

Statistical Analysis Plan (SAP)

Final 2.0  
18 Dec 2018  
CONFIDENTIAL

statistically significant GROUP\*TIME interaction effect, with greater reductions in MADRS scores in the TS-121 groups compared to placebo, will be interpreted as indicating efficacy.

The following is example SAS programming code that will be used to fit the analysis of covariance model:

```
Proc Mixed Method = REML;  
    Class GROUP;  
    Model Change = Baseline GROUP TIME GROUP*TIME  
        / solution ddfm=kenwardroger;  
    lsmeans GROUP / pdiff alpha=0.05 cl;  
    ods output lsmeans=lsm2 tests3=t3 solution;  
  
run; quit;
```

Treatment least squares means with 95% confidence intervals will be reported and also slope estimates for the baseline and TIME covariates [Table 14.2.2.5]. Model details will be presented in a statistical appendix.

### **6.3.13.2 Secondary Endpoints**

The MADRS responder status, indicating  $\geq 50\%$  reduction in total score from baseline (Visit 3 assessment) will be listed [Listing 16.2.6.1.1] and the number and percentage responders will be summarized by treatment and visit [Table 14.2.2.6]. Percentage responders at each visit will be calculated relative to number of patients evaluated.

The Clinical Global Impression Severity (CGI-S) and CGI Improvement (CGI-I) will be presented in a listing with CGI-S change from baseline and CGI-I-Improver status, indicating (“Very much improved” or “Much improved”) [Listing 16.2.6.2]. The CGI-S score and score change from baseline will be presented in a descriptive summary table [Table 14.2.3.1]. The CGI-I summary by treatment group and visit will include score frequencies and the mean and median CGI-I scores [Table 14.2.3.2].

Treatment group mean (+/- SE) CGI-S score and score change from baseline will be plotted versus treatment [Figure 14.2.3.1 and Figure 14.2.3.2].

Hamilton Anxiety Scale (HAM-A) total score, total score change from baseline and item scores will be presented in a listing [Listing 16.2.6.3]. A descriptive summary table will be presented

# Statistical Analysis Plan

Taisho Pharmaceutical R&D Inc.  
Protocol TS121-US201

Statistical Analysis Plan (SAP)

Final 2.0  
18 Dec 2018  
CONFIDENTIAL

for HAM-A total score and total score change from baseline (n, mean, SD, SE, CV%, minimum, median and maximum) by treatment and visit [Table 14.2.4.1]. A summary table will be presented for each item response of HAM-A, with score frequencies and the mean and median scores [Table 14.2.4.2]. Treatment group mean (+/- SE) HAM-A observed and change from baseline will be plotted versus treatment [Figure 14.2.4.1 and Figure 14.2.4.2].

Symptoms of Depression Questionnaire (SDQ) total score, total score change from baseline and item scores will be listed [Listing 16.2.6.4]. A descriptive summary table will be presented of total score observed and change from baseline results [Table 14.2.5.1] and a summary table of each item with the mean and median scores [Table 14.2.5.2]. Treatment group mean (+/- SE) SDQ total score and change from baseline will be plotted versus treatment [Figure 14.2.5.1 and Figure 14.2.5.2].

With respect to the secondary qualitative outcome variables, the MMRM/non-parametric methods described above will also be used to compare the difference among the three treatment groups for each secondary endpoint depending on the distribution of the data.

Changes from Baseline (Visit 3) to Week 6/EOT will be assessed for the following:

- CGI-S score [Table 14.2.3.3 LSmeans, Table 14.2.3.4 Type 3 tests]
- HAM-A total score [Table 14.2.4.3 LSmeans, Table 14.2.4.4 Type 3 tests]
- SDQ score [Table 14.2.5.3 LSmeans, Table 14.2.5.4 Type 3 tests]

The Pearson Chi-square test will be used to compare the difference between active treatment groups and the placebo group for the following secondary endpoints evaluated at Week 6/EOT. The 95% confidence interval (asymptotic calculation) for each treatment difference, TS-121 - Placebo, of percentage responders will also be reported.

- Percentage of MADRS responders ( $\geq 50\%$  reduction in total score) [Table 14.2.2.6]
- Percentage of CGI-I improvers (“Very much improved” or “Much improved”) [Table 14.2.3.2]

### ***6.3.13.3 Multiple Imputation for Missing Visits***

Multiple imputation method for missing visits will be performed for primary and secondary efficacy endpoints and the summary of treatment differences at Week 6/EOT will be presented as a sensitivity analysis.

# Statistical Analysis Plan

Taisho Pharmaceutical R&D Inc.  
Protocol TS121-US201

Statistical Analysis Plan (SAP)

Final 2.0  
18 Dec 2018  
CONFIDENTIAL

The following example SAS programming multiple imputation (MI) code will be used to assess pattern of missing visits:

```
Proc MI Nimpute=0;  
    Var GROUP TRT10 TRT50 BASE WEEK2 WEEK4 WEEK6 FOLLOW;  
run;
```

The indicator variables TRT10 (1 for TS-121 10 mg and otherwise 0) and TRT50 (1 for TS-121 10 mg and otherwise 0) are equivalent to the GROUP treatment classification variables.

The following MI code will be used to create a set of imputation data sets.

```
Proc MI Seed=xxxxx Nimpute=x out=impute_1 round= . . . .1 .1 .1 .1 ;  
    EM INITIAL = AC MAXITER=25 CONVERGE=0.00001;  
    Var TRT10 TRT50 BASE WEEK2 WEEK4 WEEK6 FOLLOW;  
run;
```

The number of imputed data sets (Nimpute) will be set to have relative efficiency > 95% for each imputed variable. This number is expected to be < 10.

The MMRM of Section 6.3.13.1 is then run by imputation number to generate two data sets: The model parameters (solutionF, solution for model fixed effects) and the treatment by visit mean differences. Only the set of treatment mean differences used to evaluate the Week 6/EOT treatment mean differences (GROUPDIF1-GROUPDIF2: D50-placebo, D10-placebo, D50-D10) will be sorted by GROUPDIF1, GROUPDIF2 and imputation number.

The following example SAS programming code will be used to evaluate the Week 6/EOT treatment mean differences (D50-placebo, D10-placebo, D50-10):

```
Proc Mianalyze Data=Diff(keep=GROUPDIF1 GROUPDIF2 Est_diff SE_diff) Edf=xx;  
    By GROUPDIF1 GROUPDIF1;  
    Modeleffects Est_diff;  
    Stderr SE_diff;  
    Ods Output Parameterestimates=Est_diff1 VarianceInfo = SE_diff1;  
run;
```

The following example SAS programming code will be used to evaluate the solution for model fixed effects.

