# Statistical Analysis Plan

Taisho Pharmaceutical R&D Inc.  
Protocol TS121-US201

Final 2.0  
18 Dec 2018  
CONFIDENTIAL

Statistical Analysis Plan (SAP)

assessment and inventory of symptoms: State versus Trait; Assessability; Face validity; Ecological validity; and Rule of three Ps (pervasive, persistent, and pathological) (SAFER) for confirmation of placebo lead-in eligibility. Results will be communicated to the site prior to Visit 2.

Visit 2 (Start of Placebo Lead-In): Following initial eligibility confirmation, qualified patients will return to the site initiating a 2-week, single-blind placebo lead-in period. An ophthalmologist will conduct a thorough eye examination (including slit lamp under mydriasis). Patients will schedule another phone call for central rater assessments (Visit 2.1), and Visit 3 will be scheduled.

Visit 2.1 (End of Placebo Lead-In): Response to placebo will be assessed using HAM-D by a central rater. The current HAM-D score and change in HAM-D score from Visit 1.1 to Visit 2.1 will be used to determine eligibility.

Visit 3 (Baseline): After completing the placebo lead-in period, patients will return to the site for baseline evaluations. Following confirmation of eligibility, patients will be randomly assigned to receive TS-121 10 mg, 50 mg, or placebo in a 1:1:1 ratio. Patients will be instructed to continue taking investigational product once-daily in the morning and to maintain their current ADT.

Visits 4 (Week 2) and 5 (Week 4): Patients will return to the site for safety and efficacy assessments, dosing compliance, drug accountability and dispensing of a new supply of investigational product. Compliance with the dosing schedule will be assessed. Visit 5 and Visit 6 will be scheduled.

Visit 6 (Week 6): Patients will return to the site for end-of-treatment safety (including ophthalmological examination), efficacy, pharmacokinetic, and exploratory pharmacodynamic assessments and final drug accountability.

End of Treatment (EOT): The EOT visit is Visit 6 for patients who complete treatment and is the last assessment closest to the last treatment day for patients who discontinued from treatment early or failed to complete Visit 6.

Visit 7 (Follow-up): Patients will return to the site for a follow-up evaluation of safety (including ophthalmological examination) and efficacy assessments approximately two weeks after Visit 6.

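### SAP 6.3.13.3 codes the 50 mg indicator as 10 mg and repeats a variable in the pooling BY statement; if followed literally, the multiple-imputation estimate for 50 mg versus placebo would be wrong, while the primary MMRM is unaffected

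*SAP*

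**What the plan says.** SAP 6.3.4 and 6.3.13.3 plan a multiple-imputation analysis of the Week 6/EOT differences as a sensitivity analysis, "using all patients with a baseline score, including patients with no post baseline assessment". The steps in 6.3.13.3 that matter here are these.

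- **Indicators.** TRT10 is 1 for TS-121 10 mg and otherwise 0. The same sentence then gives "TRT50 (1 for TS-121 10 mg and otherwise 0" and says that the two indicators "are equivalent to the GROUP treatment classification variables".
- **Imputation step.** The variable list is "Var TRT10 TRT50 BASE WEEK2 WEEK4 WEEK6 FOLLOW". GROUP appears only in the preceding step, which has zero imputations and only describes the pattern of missing visits.
- **Contrasts.** The MMRM is refitted to each imputed data set. Three Week 6/EOT differences are kept, each labelled GROUPDIF1 minus GROUPDIF2: 50 mg minus placebo, 10 mg minus placebo, and 50 mg minus 10 mg. They "will be sorted by GROUPDIF1, GROUPDIF2 and imputation number".
- **Pooling step.** The example code for PROC MIANALYZE reads "By GROUPDIF1 GROUPDIF1".

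No other part of the SAP corrects either line.

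**The concern.** Two identical columns cannot code three arms. With TRT50 defined as written, 50 mg and placebo both carry the code 0/0, and no other treatment variable is in the imputation model. Missing values in these two arms would be drawn from one common model.

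In the pooling step, 50 mg is GROUPDIF1 in two of the three contrasts. A BY statement without GROUPDIF2 puts both contrasts in one group and treats them as repeated imputations of one quantity.

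Both errors fall mainly on 50 mg versus placebo. The MI table could then disagree with the primary MMRM for a coding reason, and the gap could be read as sensitivity to missing data. The same MI method is applied to the secondary endpoints analysed by MMRM, so the CGI-S, HAM-A and SDQ tables can carry the same errors. The study's stated use is to estimate effect size for later studies, so a distorted estimate matters.

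**Working it through.** The plan gives no figure to reproduce. SAP section 5 says the sample size does not come from a power calculation, and the documents give no SD, effect size or dropout rate. The arm size of 60 is from the protocol synopsis; the other numerical inputs below are assumptions, except that 6.3.13.3 expects fewer than 10 imputations.

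**Pooling error**

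Let d50 and d10 be the two differences from placebo and m the number of imputations. Ignore imputation variance within each contrast. The 50 mg group then holds m rows at d50 and m rows at d50 − d10.

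- Pooled estimate: [m·d50 + m·(d50 − d10)]/(2m) = d50 − d10/2.
- Between-row variance: B = 2m·(d10/2)²/(2m − 1).
- Total variance: T = W + (1 + 1/(2m))·B.

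Take SD 9.3, so SE = 9.3 × √(2/60) = 1.70 and W = 2.89, with m = 5.

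- *Both doses at −4.* Estimate −4 + 2 = −2.0. B = 10 × 4/9 = 4.44. T = 2.89 + 1.1 × 4.44 = 7.78, so SE = 2.79. Rubin df = 9 × (1 + 2.89/4.89)² = 22.8, and the 95% CI is −7.8 to 3.8. Correct pooling gives −4.0, SE 1.70, CI −7.3 to −0.7. The code also has an Edf setting, left blank; with Edf of 120 to 170, df is about 15 to 17 and the CI about −7.9 to 3.9.
- *10 mg at −2, 50 mg at −4.* Estimate −3.0. B = 10 × 1/9 = 1.11. T = 2.89 + 1.22 = 4.11, so SE = 2.03.
- *True 10 mg effect zero.* There is no bias on average. The estimated d10 in one trial is still not exactly zero, so the SE still rises. A simulation with 60 per arm and 20% dropout gave 2.03 against 1.83.

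Ten mg minus placebo is alone in its BY group and is unchanged. Fifty mg minus 10 mg has no row.

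**Indicator error, if the procedure runs**

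Seven columns of which two are identical have a covariance matrix of rank 6. SAS may warn or stop; this was not tested. The figures here treat the duplicate column as dropped.

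A rough ceiling comes first. Suppose a share p of each arm lacks Week 6 and earlier visits carry no information. Missing values in 50 mg and placebo are then drawn around the mean of the two arms, which is placebo + d50/2.

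- 50 mg minus placebo becomes (1 − p)·d50.
- 10 mg minus placebo becomes d10 − p·d50/2, because the placebo mean has moved.

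With both doses at −4 this gives −3.52 and −3.76 at p = 12%, and −3.00 and −3.50 at p = 25%. Earlier visits preserve part of the arm difference, so the actual shift is smaller.

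A large-sample simulation used 400,000 per arm and SDs of 5.5, 7.5, 8.5 and 9.3 at baseline and Weeks 2, 4 and 6. AR(1) correlation was 0.6 or 0.75, with 50, 80 and 100% of the effect at Weeks 2, 4 and 6. Random monotone dropout was even or late. With Week 6 left missing it gave:

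| Dropout | 50 mg minus placebo | 10 mg minus placebo | 50 mg row, both errors |
|---|---|---|---|
| 12% | −3.63 to −3.83 | −3.82 to −3.90 | −1.72 to −1.88 |
| 25% | −3.26 to −3.55 | −3.62 to −3.78 | −1.45 to −1.66 |

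- Shrinkage for 50 mg: 0.17/4 to 0.37/4, about 4–9%, at 12% dropout; 0.45/4 to 0.74/4, about 11–19%, at 25%.
- The last column follows from the pooling formula, for example −3.63 + 3.82/2 = −1.72.

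A separate simulation used 60 per arm, SD 9, both doses at −3 and 9 imputations. The indicator error alone gave −2.81, −2.60 and −2.37 for 50 mg at 10, 20 and 30% dropout. Correct coding gave −3.03, −3.04 and −3.06, so the loss was about 7, 14 and 23%.

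The effect is smaller if WEEK6 holds the EOT value of SAP section 1, which "is the last assessment closest to the last treatment day for patients who discontinued from treatment early". Only patients with no post-baseline visit then need a Week 6 value imputed. The 50 mg shrinkage is 0–4% at 12% dropout and 0–9% at 25%, and nil if every patient has a post-baseline visit.

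**The case against.** The strongest reply is that these are two typing slips whose intent is plain in the same section. The variable is named TRT50, and two copies of a 10 mg indicator cannot be equivalent to GROUP. The sort order and the keep= option in the pooling step both name GROUPDIF2. The pooling code is labelled an example. The block also has unfilled settings for the seed, the number of imputations and Edf, so a programmer must edit it before it runs. A singular matrix may stop the imputation, and two rows where three are promised would be noticed. The MADRS MI table (14.2.2.3.1) is not marked top-line.

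All of that stands, and it limits the weight of the point. It does not remove it. The SAP says the example code will be used. The TRT50 error is in the prose definition on which otherwise correct imputation code depends.

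A reader might infer three stronger things that the documents do not support.

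- *The reported 50 mg MI result will be distorted.* That holds only if the text is followed literally and the procedure runs.
- *The primary result is compromised.* The primary MMRM in 6.3.13.1 uses GROUP directly and no imputed data.
- *The MI is the only analysis that takes in patients with baseline data alone.* The analysis of covariance in 6.3.13.1, reported in top-line Table 14.2.2.5, may include them too.

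**Conclusion.** Both errors are in the final SAP and should be corrected.

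The pooling error is exact in form: the 50 mg row equals d50 − d10/2, with an inflated SE unless d10 is zero, and the 50 mg minus 10 mg row is lost. When the two doses work equally well, the 50 mg estimate is halved. This does not depend on dropout.

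The indicator error is smaller and conditional. It requires the procedure to run despite the singular covariance, grows with dropout, and can vanish if Week 6/EOT is filled with the last assessment. It shifts 10 mg versus placebo by about half as much as 50 mg or less when the doses are equal. All its sizes rest on assumed SDs, effects, correlations and dropout, so they show direction and order of magnitude only.

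The reach is Table 14.2.2.3.1 and, for the indicator error only, Table 14.2.2.4.1, with their CGI-S, HAM-A and SDQ counterparts.

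**What to change.** In SAP 6.3.13.3:

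1. Define TRT50 as 1 for TS-121 50 mg and otherwise 0.
2. Change the pooling statement to `By GROUPDIF1 GROUPDIF2;`.

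With both changes, the simulation with 60 per arm recovers the assumed values. At 20% dropout with both doses at −3, it gives −3.04 for 50 mg versus placebo, −2.96 for 10 mg versus placebo and −0.08 for 50 mg versus 10 mg, each with SE 1.83. The cost is one prose definition and one code line, with no statistical downside.
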